1.2. Rationale for the study and study design

This study will be conducted to allow for a safe exit from the HPV-015 study, ensuring that women who are at risk of developing a gynaecological lesion are medically monitored.

Study subjects enrolled in the control arm of HPV-015 study may have been infected with the HPV types included in the vaccine during the study. All subjects may have been exposed to other high-risk HPV types.

The current study will provide annual oncogenic HPV DNA testing and cervical cytology examination for a subset of HPV-015 subjects, who at their concluding HPV-015 study visit:

- displayed normal cervical cytology but tested positive for oncogenic HPV infection
- were pregnant so that no cervical sample could be collected

For eligible subjects, the duration of this gynaecological follow-up will be up to a maximum of four years after the subjects' concluding HPV-015 study visit, since most cervical lesions develop within four years of infection and most oncogenic HPV infections are estimated to clear within two years [Trottier, 2008].

If very few subjects are eligible for this study at one HPV-015 study site and if adequate gynaecological follow-up care is available through the local health care system, these subjects may be referred to the local health care system, provided that ethical committee approval is obtained by the responsible investigator.

The initial protocol of the HPV-015 trial included a three year efficacy follow-up. The HPV-015 protocol amendment 3 and 4 extended the HPV-015 trial by one and up to a maximum of three additional years, respectively. Subjects may however decide to conclude their participation in the HPV-015 study at Visit 9, Visit 11 or at the last study visit in HPV-015 planned under protocol amendment 4.

Note that subjects enrolled in this study can also concurrently participate in a GSK Biologicals study to receive cross-over vaccination.

This study is not intended to collect long-term efficacy, immunogenicity or safety follow-up data. Long-term data for GSK Biologicals' HPV vaccine will be obtained through other studies.

1.2.1. Rationale for the use of placebo

Not applicable.

2. STUDY OBJECTIVES

[figure not shown]
- To provide clinical management and, if required, treatment to subjects who at their concluding HPV-015 study visit displayed normal cervical cytology but tested positive for oncogenic HPV infection or who were pregnant at their concluding visit of the HPV-015 study so that no cervical sample could be collected

Refer to Section 10.1 for the definition of the study endpoints.

3. STUDY DESIGN OVERVIEW

An overview of the study design is presented in Figure 1.

Figure 1 Study visits and study procedures

*Subjects with two positive oncogenic HPV DNA tests or one cervical cytology reading \geq ASC-US (atypical squamous cells of undetermined significance) positive for oncogenic HPV DNA or one cervical cytology reading \geq LSIL (low grade squamous intraepithelial lesion) will be referred for colposcopy evaluation according to the clinical management algorithm. Oncogenic HPV tests (HCII) will only be performed on normal and ASCUS cytological samples.

[figure not shown]
** Study conclusion, see dotted line (-), will occur after any given visit that required treatment of cytological abnormality, any given visit with a negative oncogenic HPV DNA test and normal cervical cytology or the closing of study activities related to Visit 4.

- Experimental design:** A phase IIIb, open, multi-centre study with one group.
- Treatment allocation:** None.
- Blinding:** Open.
- HPV-015 concluding visit:** Subjects who participated in the HPV-015 study may decide to conclude their participation in the HPV-015 study at Visit 9, Visit 11 or at the last study visit in HPV-015 planned under protocol amendment 4.

- **Treatment groups:** One study group consisting of a subset of HPV-015 subjects who at their concluding HPV-015 study visit:
 - displayed normal cervical cytology but tested positive for oncogenic HPV infection
 - were pregnant so that no cervical sample could be collected at that visit

The study eligibility algorithm is presented in [Figure 2](#).

Figure 2 HPV-062 EXT:015 study eligibility algorithm

- **Vaccination schedule(s):** None.
- **Control:** None.
- **Type of study:** Gynaecological follow-up extension study of a subset of HPV-015 study subjects.
- **Data collection:** Remote Data Entry (RDE).
- **Duration of the study:** Maximum of four years for each subject.
- **Study visits per subject:** Up to four scheduled visits at approximately Months 12, 24, 36 and 48 after each subject’s concluding HPV-015 study visit.

Subjects are eligible to join the study at any visit.

- **Study procedures:**

Subjects will enter the study approximately one year after their HPV-015 concluding visit. Annual visits will be scheduled for a maximum study duration of approximately four years.

At each visit, a gynaecological examination will be performed and cervical liquid-based cytology samples will be collected for cervical cytology examination and oncogenic HPV DNA testing, if the cytology reading is normal or ASCUS.

The presence of oncogenic HPV infection will be determined by the Hybrid Capture® II (HCII) test, which detects HPV DNA types 16, 18, 31, 33, 35, 39, 45,

51, 52, 56, 58, 59 and 68 [Vernick, 2003, Digene Corporation 2002]. Cervical cytology examination will be performed using the ThinPrep®Pap test.

Continued study participation as well as further referral/treatment will be based on the test results from each visit, and will be aligned with the clinical management algorithm which is aligned with the 2009 American Society for Colposcopy and Cervical Pathology (ASCCP) guidelines for use of HPV DNA testing as an adjunct to cytology for cervical cancer screening in women 30 years or older.

The following clinical management algorithm will be applied, refer to [Figure 3](#).

- Subjects with normal cervical cytology and who are oncogenic HPV DNA negative, will end their participation in the study.
- Subjects with normal cervical cytology, but who are oncogenic HPV DNA positive in one single test, will be asked to return at the next study visit.
This outcome will only be applicable to subjects who were pregnant at their concluding HPV-015 study visit so that no cervical sample could be collected at that visit.
- Subjects with normal cervical cytology, but who are oncogenic HPV DNA positive in two subsequent tests, will be referred to colposcopy. The result of the subjects' last HPV-015 study visit will be taken into account at Visit 1.
- Subjects with a single cervical cytology reading of \geq ASC-US (atypical squamous cells of undetermined significance) positive for oncogenic HPV DNA will be referred to colposcopy.
- Subjects with a single cervical cytology reading of \geq LSIL (low grade squamous intraepithelial lesion) will be referred to colposcopy.

Please note that a missing result for HCII will be managed as oncogenic HPV positive.

In case of referral for colposcopy, the post-colposcopy follow-up strategies are:

- If no lesion is detected or the detected lesion does not require any treatment, subjects will be asked to return at the next study visit.
- If a lesion that requires treatment is detected, the subject should be referred to treatment according to local medical practice. Any further management following local cervical therapy for cervical lesions will be handled according to local medical practice within the local health care system. After treatment, the subject's participation in the study will end.

[figure not shown]
As management algorithms cannot define every clinical situation, it is the investigator's (or his/her designee's) responsibility to exercise appropriate clinical judgement in the medical management of each individual case.

Once their study participation ends, all subjects should be referred to their local health care system.

Subjects who have not developed cervical lesions by the end of the study, but who are still positive for oncogenic HPV infection, should be informed of the potential

risks of being positive for oncogenic HPV DNA, and the importance of continued follow-up.

Figure 3 Clinical management algorithm

HPV DNA test (HCII) = Hybrid Capture® II test detecting HPV types 16, 18, 31, 33, 35, 39, 45, 51, 52, 56, 58, 59 and 68. Specimens will be reported as “Quantity Not Sufficient” (QNS) in the case where there is an inadequate amount of cells for HCII and preferentially, a repeat sample will be collected. Missing HCII test results should be managed as oncogenic HPV positive
* = The result of the subject’s concluding HPV-015 study visit will be taken into account. Subjects who were pregnant at that visit so that no cervical sample could be collected, and who display normal cytology but are positive for oncogenic HPV DNA at Visit 1, will return for the next study visit.
** = Colposcopy and/or colposcopy-directed biopsies will be performed according to local medical practice.
§ = Oncogenic HPV tests (HCII) will only be performed on normal and ASCUS cytological samples.

• Study visit activities and gynaecological follow-up reporting

- Gynaecological examination at Visit 1, Visit 2, Visit 3 and Visit 4.
- Collection of cervical liquid-based cytology samples at Visit 1, Visit 2, Visit 3 and Visit 4 for cervical cytology examination and oncogenic HPV DNA testing, if the cytology reading is normal or ASCUS.
- Referral to colposcopy according to protocol clinical management algorithm, if required.
- Conduct of colposcopy, colposcopy directed biopsies and local cervical therapy according to local medical practice, if required.
- Recording of colposcopic referral according to management algorithm, if required.

- Recording of treatment referrals according to local medical practice, if required.
- **Safety reporting:**
 - All fatal SAEs will be reported.
 - All SAEs assessed as being possibly related to study participation will be reported.
 - All SAEs assessed as being possibly related to a concurrent GSK medication will be reported.
 - Withdrawal from the study due to adverse events (AEs) or SAEs will be reported.

No other AEs or SAEs for HPV-015 study subjects will be reported in this study. AEs and SAEs related to the vaccine administered in the HPV-015 trial should be reported as part of the HPV-015 study, as described in the HPV-015 study protocol.

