- Subjects with normal cervical cytology, but who are oncogenic HPV DNA positive in one single test, will be asked to return at the next study visit.
This outcome will only be applicable to subjects who were pregnant at their concluding HPV-015 study visit so that no cervical sample could be collected at that visit.
- Subjects with normal cervical cytology, but who are oncogenic HPV DNA positive in two subsequent tests, will be referred to colposcopy. The result of the

CONFIDENTIAL

113617 (HPV-062 EXT:015)
Administrative Change 1

subjects' concluding HPV-015 study visit will be taken into account at Visit 1.

- Subjects with a single cervical cytology reading of \geq ASC-US (atypical squamous cells of undetermined significance) positive for oncogenic HPV DNA will be referred to colposcopy.
- Subjects with a single cervical cytology reading of \geq LSIL (low grade squamous intraepithelial lesion) will be referred to colposcopy.

Please note that a missing result for HCII will be managed as oncogenic HPV positive.

In case of referral for colposcopy, the post-colposcopy follow-up strategies are:

- If no lesion is detected or the detected lesion does not require any treatment, subjects will be asked to return at the next study visit.
- If a lesion that requires treatment is detected, the subject should be referred to treatment according to local medical practice. Any further management following local cervical therapy for cervical lesions will be handled according to local medical practice within the local health care system. After treatment, the subject's participation in the study will end.

As management algorithms cannot define every clinical situation, it is the investigator's (or his/her designee's) responsibility to exercise appropriate clinical judgement in the medical management of each individual case.

Once their study participation ends, all subjects should be referred to their local health care system.

Subjects who have not developed cervical lesions by the end of the study, but who are still positive for oncogenic HPV infection, should be informed of the potential risks of being positive for oncogenic HPV DNA and the importance of continued follow-up.

- **Study visit activities and gynaecological follow-up reporting**
 - Gynaecological examination at Visit 1, Visit 2, Visit 3 and Visit 4.

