4.3. Exclusion criteria for enrolment

The following criteria should be checked at the time of study entry. If **ANY** exclusion criterion applies, the subject must not be included in the study:

- A subject who at the HPV-015 concluding study visit displayed normal cervical cytology and who was negative for oncogenic HPV infection at that visit.
- A subject who at the HPV-015 concluding study visit had a cervical lesion at that visit or who had a cervical lesion that required treatment at her HPV-015 exit colposcopy.
- A subject for whom the cervical cytology results from the concluding HPV-015 study visit were unavailable for reasons other than pregnancy.

If at the time of enrolment the subject experiences heavy bleeding (menstruation or other) or heavy vaginal discharge, the pelvic exam cannot be performed. Enrolment will be deferred until condition is resolved according to investigator's medical judgment.

If the subject is pregnant at the time of enrolment, enrolment should be deferred until at least 3 months after the pregnancy has been completed. The subject should attend the next protocol scheduled visit (i.e. within the protocol windows). Subjects are eligible to enter the study at any visit.

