Reporting of AEs and SAEs leading to study withdrawal	●	●	●	●
Study Conclusion	● [§]	● [§]	● [§]	●

● is used to indicate a study procedure that requires documentation in the individual eCRF.

○ is used to indicate a study procedure that does not require documentation in the individual eCRF.

*Subjects are eligible to join the study at any visit

§ A subject who has been referred to local treatment or who displays normal cervical cytology and who tests negative for oncogenic HPV DNA will exit the study.

Table 2 Intervals between study visits

Interval (Months after HPV-015 concluding visit (Visit 9, Visit 11 or last HPV-015 study visit as planned in the HPV-015 protocol amendment 4))	Length of interval (days)	Recommended interval between scheduled visits (days)*
Concluding visit HPV-015 → Visit 1 HPV-062 (Month 12)	183-547	365
Concluding visit HPV-015 → Visit 2 HPV-062 (Month 24)	548-912	730
Concluding visit HPV-015 → Visit 3 HPV-062 (Month 36)	913-1277	1095
Concluding visit HPV-015 → Visit 4 HPV-062 (Month 48)	1278-1642	1460

*There should be a minimum of 183 days between two consecutive study visits.

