5.8.2.6. Recording of referral to colposcopy and treatment (if applicable)

- Record referral for colposcopy according to clinical management algorithm, if applicable. The result of the subjects' last HPV-015 study visit will be taken into account. It is recommended that colposcopy is performed within 30 days of referral.
- Record treatment referral, if applicable.

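### Does tying the HPV-015 exit result to Visit 1 leave some late joiners without a colposcopy rule?

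*Protocol*

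**What the plan says.** The rule on the exit result appears in several places, in two forms.

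**With Visit 1 named.** In the Protocol section 3 algorithm, women with normal cytology who are "oncogenic HPV DNA positive in two subsequent tests, will be referred to colposcopy". The next sentence reads "The result of the subjects' last HPV-015 study visit will be taken into account at Visit 1". The Protocol synopsis has the same rule ("subjects' concluding HPV-015 study visit will be taken into account at Visit 1"), and SAP section 2 repeats the section 3 sentence.

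**With no visit named.** Protocol section 5.8.2.6, on recording referrals, says "The result of the subjects' last HPV-015 study visit will be taken into account" and stops there. The first sentence of the Figure 3 footnote, in both documents, is also unlimited: "concluding HPV-015 study visit will be taken into account. Subjects who were pregnant at that visit" spans the end of that sentence and the start of the next, which concerns women pregnant at exit.

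**The alternative branch.** A woman with normal cytology and a single positive test returns at the next visit, but this is restricted: "This outcome will only be applicable to subjects who were pregnant at their concluding HPV-015 study visit so that no cervical sample could be collected".

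**Late entry.** The Table 1 footnote in Protocol section 5.7 says "Subjects are eligible to join the study at any visit". Section 4.3 gives one route, deferral of a woman who is pregnant at enrolment: "The subject should attend the next protocol scheduled visit (i.e. within the protocol windows). Subjects are eligible to enter the study at any visit". Table 2 places Visit 1 at days 183 to 547 after the concluding HPV-015 visit.

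**The concern.** Visit 1 is a calendar slot in this study, not whichever visit a woman attends first. Someone whose first attendance falls on day 548 or later enters at Visit 2, 3 or 4 and never has a Visit 1. If her HPV-015 result counts at Visit 1 alone, it never counts for her.

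Suppose she was HPV positive at exit and, on joining late, has normal cytology and a positive Hybrid Capture II test. A missing result is managed as positive, so it leads to the same place. On the strict reading she has one counted positive test. That is too few for the two-test branch, and the single-positive branch is reserved for women who were pregnant at exit. Section 5.8.2.6, by contrast, would count her exit result.

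Clinical management is the study's only objective, and referral to colposcopy is one of four endpoints. If sites read the text differently, the same woman could be handled differently at two centres. The referral counts that SAP section 6.1.2 tabulates for each visit could then mix two practices at Visits 2 to 4.

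**Working it through.** No sample size, power or error rate bears on this point; Protocol section 10.2 says the study is descriptive. The check is to follow each type of woman through the written branches.

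**Inputs.** Exit status is either normal cytology and HPV positive, or pregnant with no sample (section 4.2). Entry may be at Visit 1 (days 183–547), Visit 2 (548–912), Visit 3 (913–1277) or Visit 4 (1278–1642), from Table 2. The branches are those in section 3.

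| Exit status | Entry visit | First in-study result | Written outcome |
|---|---|---|---|
| Either | Any | Normal, HPV negative | Participation ends |
| Either | Any | ASC-US with HPV positive or missing, or LSIL or worse | Colposcopy, whatever the exit result |
| HPV positive | Visit 1 | Normal, HPV positive or missing | Colposcopy, because the exit result counts |
| Pregnant | Any | Normal, HPV positive or missing | Return at next visit |
| HPV positive | Visit 2, 3 or 4 | Normal, HPV positive or missing | Depends on the reading |

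Only the last row is in question. Its entry window runs from day 548 to day 1642, that is 548 / 30.44 = 18.0 to 1642 / 30.44 = 53.9 months after the exit test.

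**The last row under each reading.**

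1. *The exit result counts at entry* (section 5.8.2.6 and the first sentence of the Figure 3 footnote). She has two positive tests, so the two-test branch applies and she is referred. The Figure 1 footnote also sends two positive tests to colposcopy with no visit limit.
2. *The exit result counts only at Visit 1.* She has one counted positive test. The two-test branch does not apply and the return branch is closed to her, so no branch applies.

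The second reading does not send her anywhere else. It gives no outcome at all. The comparison is therefore between one written disposition and silence.

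**Does the text require the second reading?** Four features say it does not.

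- The algorithm names Visit 1 but does not say that the exit result counts only there. Section 3 also describes entry as happening about a year after exit, so naming Visit 1 describes the usual entry.
- The restriction on the return branch has no visit limit. It assumes that a woman who was positive at exit does not count as single-positive, whenever she joins.
- Section 5.8.2.6 tells sites to record referrals in line with the algorithm, so it applies that algorithm and is not a rival rule. Table 1 schedules this recording at all four visits.
- The Figure 3 footnote also mentions Visit 1 when it describes the return of women pregnant at exit, yet the corresponding bullet in section 3 has no such limit. The row for pregnant women above relies on the unlimited text. The same treatment of the last row leaves no gap.

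**Number of women.** This would need the share of the approximately 1500 eligible who enter after Visit 1, the share of those who were HPV positive at exit, and the share with normal cytology and a positive or missing test at entry. Neither document gives any of the three, so no figure can be calculated. With two exit groups and four entry visits, 3 of the 8 combinations fall in the last row, but that counts table cells and says nothing about how many women are in them.

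**The case for a change.** The best argument for acting is that a multi-centre study should not leave a colposcopy decision to inference. Three places name Visit 1, late entry is planned, and a busy site may consult the algorithm without section 5.8.2.6 or a footnote. Where the algorithm is silent, section 3 leaves the case to the investigator's judgement, and judgement can differ between sites. It can also be said that section 5.8.2.6, precisely because it applies the algorithm, ought to restate the rule in the same terms.

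Much of this stands. The wording is uneven, one row of the table depends on how it is read, and identical sentences would be tidier. What does not stand is the step to inconsistent results. No passage offers these women a different outcome that a site could follow. A site that sees the gap can look to section 5.8.2.6 and Figure 3, and investigator judgement is the protocol's own provision for cases the algorithm does not define.

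A related remark is that the Figure 1 footnote asks for two positive tests where the algorithm asks for two subsequent ones. These could differ for a woman pregnant at exit whose results run normal and positive, then ASC-US and negative, then normal and positive. That footnote defers to the algorithm, however, so the difference is editorial.

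**Conclusion.** The concern identifies a genuine wording gap, but nothing in the plan has to change because of it. It affects one subgroup: women HPV positive at exit, entering at Visit 2, 3 or 4, with normal cytology and a positive or missing Hybrid Capture II result. For that subgroup the documents supply one branch and no competing one.

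The analysis is unaffected in form. Referral to colposcopy is tabulated as recorded, and the endpoint can be counted under either reading. No stated figure or descriptive conclusion is shown to be wrong. A woman-level size cannot be given.

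This rests on two assumptions. First, sites read the algorithm together with section 5.8.2.6 and the footnotes. Second, the drawing of Figure 3 does not itself impose a Visit 1 limit. It is not reproduced in the text available here, and Protocol sections 5.4.3 and 5.5 make it the description of how all cytology results are managed, so it may settle the point outright.

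If the documents are reopened for another reason, the sponsor should reconcile the sentences to one wording. That is housekeeping, and nothing here says which referral rule is right.
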